Unique Protocol ID: 13011998

Brief Title: Volatilome and Single-Lead Electrocardiogram Optimize Ischemic Heart Disease Diagnosis
Using Machine Learning Models

Official Title: Biomarkers of the Exhaled Breath and Single-Lead Electrocardiography in the Diagnosis
of Myocardial Ischemia

NCT number: NCT06181799

Document date: 17.06.2024

Study Protocol

1. Relevance of the topic.

The relevance of the proposed scientific problem is beyond doubt. Cardiovascular disease (CVD) is the leading cause of mortality and morbidity in the 21st century, despite modern progress in therapeutic strategies and technologies [1]. Unfortunately, every second person worldwide dies from cardiovascular event. According to the World Health Organization data published in 2021, it is known that in 2019, 17.9 million people died from CVD, which is 32% of all deaths worldwide. Cardiovascular diseases (CVD) are the leading cause of death in the Russian Federation and account for about 54 % of all cases. The leading position among these diseases is occupied by ischemic heart disease, the annual mortality from ischemic heart disease is 38% [2,3].

For several decades, there have been active attempts to develop reliable diagnostic methods for coronary heart disease applicable to mass population screening. It is known that the diagnostic accuracy of the most accessible method for detecting signs of myocardial ischemia - the stress ECG test, does not exceed 70%. In this regard, the search for various biomarkers that increase the accuracy of stress testing is a practically significant and urgent task. There is a growing interest in studying the composition of exhaled air (volatile organic compound concentrations). Exhaled air analysis using mass spectrometry (MAS) in stable coronary heart disease (CHD), as well as in the diagnosis of CHD, has not been studied and requires further development. In addition, predicting changes in lipidome and inflammasome in correlation with exhaled air (EA) analysis has also not been studied and can determine the pathogenetic basis for the development of CHD.

We analyzed various databases (PubMed, Embase, Cochrane library, China National Knowledge Infrastructure), found a limited number of works aimed at studying volatile organic compounds in exhaled air in patients with coronary heart disease. There are many descriptive works on the methodology for performing and analyzing volatile, a limited number of works devoted to the search for cardiometabolic substances in exhaled air.

The attention to the MSM BB method is also justified by the fact that the test does not require expensive consumables and is carried out within one minute, which allows this method to be used in addition to the load test, without changing the test protocol significantly.

Also, to improve the diagnosis of coronary heart disease, a single-channel electrocardiogram is used with pulse wave assessment and the ability to predict the risk of cardiovascular events using artificial intelligence algorithms.

2. Novelty of the proposed topic based on literary sources and patent documentation.

For the first time in the world, use real time method of analysis of the composition of the exhaled breath using time-of-flight mass spectrometer-proton transfer reaction- mass spectrometer-1000. There is no study reporting changes in the analysis of exhaled air using this method in patients with ischemic heart disease, confirmed by stress induced myocardial perfusion defect.

For the first time in the world, single-channel ECG with pulse wave function analysis using machine learning models will be performed to predict a positive test result for ischemic heart disease.

3. Objective and tasks of the planned research.

Goal:

1. To increase the diagnostic accuracy of functional tests with physical activity under the control of a 12-channel ECG with parameters for analyzing the molecular composition of exhaled air, single-channel ECG data with pulse wave function.

Tasks:

1. Assessing the diagnostic accuracy of the stress electrocardiography in the diagnosis of ischemic heart disease (AUC, Sensitivity, Specificity, Sensitivity, NPV, and PPV)

2. Analyze the volatile organic compounds of the exhaled breath in individuals with stress-induced myocardial perfusion defect on stress computed tomography myocardial perfusion imaging (CTP) with vasodilation test (adenosine triphosphate) and compare them with individuals without stress-induced myocardial perfusion defect after a physical stress test, and compare them with rest results as independent variables. Machine learning model will be used to assess the diagnostic accuracy of the exhaled breath in the diagnosis of ischemic heart disease

3. Analyze the parameters of the single-lead electrocardiogram with pulse wave function in individuals with stress-induced myocardial perfusion defect on stress computed tomography myocardial perfusion imaging (CTP) with vasodilation test and compare them with individuals without stress-induced myocardial perfusion defect as an independent variable. Machine learning model will be used to assess the diagnostic accuracy of the single-lead ECG with pulse wave function in the diagnosis of ischemic heart disease.

4. Analyzing the taken blood samples for total cholesterol, TG (mmol/L), LDL (mmol/L), LDL (mmol/L), HDL (mmol/L), and VLDL (mmol/L) in individuals with stress-induced myocardial perfusion defect on stress computed tomography myocardial perfusion imaging (CTP) with vasodilation test and comparing them with individuals without stress-induced myocardial perfusion defect as independent variables.

5. Analyzing the taken blood samples for Apolipoprotein B (g/L) in individuals with stress-induced myocardial perfusion defect on stress computed tomography myocardial perfusion imaging (CTP) with vasodilation test and comparing them with individuals without stress-induced myocardial perfusion defect as independent variables.

6. Analyzing the taken blood samples for lipoprotein (a) (mg/L) and c-RP (mg/L) in individuals with stress-induced myocardial perfusion defect on stress computed tomography myocardial perfusion imaging (CTP) with vasodilation test and comparing them with individuals without stress-induced myocardial perfusion defect as independent variables.\

7. Analyzing the taken blood samples for IL- 6 (pg/mL) in individuals with stress-induced myocardial perfusion defect on stress computed tomography myocardial perfusion imaging (CTP) with vasodilation test and comparing them with individuals without stress-induced myocardial perfusion defect as independent variables.

4. Research design.

A prospective, non-randomized, minimally invasive, cohort case-control study includes patients (men and women) aged ≥ 40 years. Participants will be recruited from 01.11.2023 to 10.06.2024 at the University Clinical Hospital No. 1 of Sechenov University, Moscow.

Once enrolled in the study, participants will be divided into two groups based on the results of a stress computed tomography myocardial perfusion (CTP) imaging with vasodilation test using the adenosine triphosphate:

- The first group is planned to include 31 people with myocardial perfusion defect on the stress computed tomography myocardial perfusion Imaging (by using contrast enhanced multi-slice spiral computed tomography (CE-MSCT) using adenosine triphosphate (ATP)).

- The second group is planned to include 49 people without myocardial perfusion defect on the stress computed tomography myocardial perfusion imaging (by using contrast enhanced multi-slice spiral computed tomography (CE-MSCT) using adenosine triphosphate (ATP)).

All patients are planned to undergo the following examinations:

1. Exhale into proton transfer reaction- time of flight-mass spectrometry-1000 for one minute using the PTR-TOF-MS-1000 device (Patients/control group come to the hospital (ate two hours before the test to avoid hypoglycemia during the stress test)/did not brush their teeth with toothpaste).

To prepare the participant for the time-of-flight mass spectrometry with proton transfer ionization method, the participant enters the office, sits on a chair in front of the device, the patient is informed that he/she needs to clasp the breathing tube with his/her lips, breathe through the nose and exhale through the mouth into the tube, which is connected to the PTR-TOF-MS-1000 device (IONICON PTR-TOF-MS - Trace VOC Analyzer, [name] (Europe)), for 1 minute.

2. After the procedure of exhaled air analysis in PTR TOF-1000, patients undergo a bicycle ergometry study, according to the Bruce protocol or the modified Bruce protocol). Then, immediately after stopping the load test, patients undergo a repeated study of exhaled air by the method of time-of-flight mass spectrometer with ionization by the proton transfer method for 1 minute, and after 3 minutes a repeated analysis of exhaled air is carried out, also for 1 minute. The obtained exhaled breath data will be analyzed using machine learning models.

3. On the morning of study enrollment, a single 10 mL venous blood sample will be collected via peripheral venipuncture using vacuum biochemical tubes from all participants. The samples will undergo centrifugation at 2000 rpm for 20 minutes to separate plasma, after which the plasma fraction was aliquoted into seven sterile tubes using calibrated pipetting systems. Each tube will be labeled with the participant's unique registration number and sample collection date, then sealed within individual bags displaying duplicated identification data externally. Samples were cryopreserved at -82 to -84°C in ultra-low temperature freezers for long-term storage. Following complete blood collection across the cohort, frozen plasma specimens will be transferred to the laboratory for quantification of total cholesterol (TC), low-density lipoprotein (LDL), very low-density lipoprotein (VLDL), high-density lipoprotein (HDL), triglycerides (TG), lipoprotein(a), apolipoprotein B (ApoB), C-reactive protein (CRP), and interleukin-6 (IL-6).

4. Before and immediately after the exercise test, all patients are scheduled to have a single-channel ECG and pulse wave recorded using a portable single-channel recorder (Cardio-Qvark) (Russia, Moscow). Single lead ECG with pulse wave parameters will be analyzed using machine learning models.

5. All participants will undergo CTP with vasodilation test.

5. The object of the study and the planned number of observations, with justification for the selection of patients.

The object of the study is 80 human.

Inclusion Criteria:

1. Age \geq 40 years;
2. Absence of acute exacerbations of psychiatric disorders or cognitive impairments that would preclude study participation;
3. Provision of written informed consent for study participation, blood sample collection, and anonymous publication of research results;
4. Pre-test probability of ischemic heart disease between 1% and 33%.

Non-inclusion criteria:

1. Pregnancy and breastfeeding;
2. Diabetes mellitus;
3. Presence of acute myocardial ischemia (acute coronary syndrome or myocardial infarction within the preceding 48 hours) or a history of myocardial infarction;
4. Active infectious or non-infectious inflammatory diseases in the acute/exacerbation phase;

5. Connective tissue diseases (regardless of disease activity);
6. Respiratory disorders (e.g., bronchial asthma, chronic bronchitis, cystic fibrosis, or other conditions associated with significant respiratory dysfunction);
7. Acute pulmonary thromboembolism involving the pulmonary artery or its branches;
8. Aortic dissection;
9. Hemodynamically significant decompensated cardiac valvular defects;
10. Active malignancy;
11. Decompensated chronic heart failure (NYHA class III-IV) or acute heart failure;
12. Neurological disorders (e.g., Parkinson's disease, multiple sclerosis, acute psychosis, Guillain-Barré syndrome);
13. Cardiac arrhythmias or conduction abnormalities contraindicating stress testing;
14. Musculoskeletal disorders precluding exercise testing (e.g., bicycle ergometry);
15. Allergy to radiocontrast agents and/or adenosine triphosphate (ATP);
16. Chronic kidney disease with an estimated glomerular filtration rate (eGFR) <30 mL/min/1.73 m² (CKD-EPI formula);
17. Severe hepatic insufficiency and/or Child-Pugh class B or C liver cirrhosis.

Exclusion Criteria:

1. Poor recording quality of single-channel electrocardiogram (ECG) and/or plethysmography data;
2. Failure to complete the stress test due to reasons unrelated to cardiac conditions;
3. Voluntary withdrawal of consent to continue participation in the study;
4. Post-enrollment development of conditions or identification of pathologies listed in the exclusion criteria.

6. Evaluated outcomes (primary endpoints).

The results in the primary are subjective and subject to the objectivity of the study.

1. Assessing the diagnostic accuracy of the stress electrocardiography in the diagnosis of ischemic heart disease (AUC, Sensitivity, Specificity, Sensitivity, NPV, and PPV)
2. Analyze the volatile organic compounds of the exhaled breath in individuals with stress-induced myocardial perfusion defect on stress computed tomography myocardial perfusion imaging (CTP) with vasodilation test (adenosine triphosphate) and compare them with individuals without stress-induced myocardial perfusion defect after a physical stress test, and compare them with rest results as independent variables. Machine learning model will be used to assess the diagnostic accuracy of the exhaled breath in the diagnosis of ischemic heart disease
3. Analyze the parameters of the single-lead electrocardiogram with pulse wave function in individuals with stress-induced myocardial perfusion defect on stress computed tomography myocardial perfusion imaging (CTP) with vasodilation test and compare them with individuals without stress-induced myocardial perfusion defect as an independent variable. Machine learning model will be used to assess the diagnostic accuracy of the single-lead ECG with pulse wave function in the diagnosis of ischemic heart disease.
4. Analyzing the taken blood samples for total cholesterol, TG (mmol/L), LDL (mmol/L), LDL (mmol/L), HDL (mmol/L), and VLDL (mmol/L) in individuals with stress-induced myocardial perfusion defect on stress computed tomography myocardial perfusion imaging (CTP) with vasodilation test and comparing them with individuals without stress-induced myocardial perfusion defect as independent variables.

5. Analyzing the taken blood samples for Apolipoprotein B (g/L) in individuals with stress-induced myocardial perfusion defect on stress computed tomography myocardial perfusion imaging (CTP) with vasodilation test and comparing them with individuals without stress-induced myocardial perfusion defect as independent variables.

6. Analyzing the taken blood samples for lipoprotein (a) (mg/L) and c-RP (mg/L) in individuals with stress-induced myocardial perfusion defect on stress computed tomography myocardial perfusion imaging (CTP) with vasodilation test and comparing them with individuals without stress-induced myocardial perfusion defect as independent variables.\

7. Analyzing the taken blood samples for IL- 6 (pg/mL) in individuals with stress-induced myocardial perfusion defect on stress computed tomography myocardial perfusion imaging (CTP) with vasodilation test and comparing them with individuals without stress-induced myocardial perfusion defect as independent variables.

7. Main stages of the research.

1. Search and recruitment of patients to participate in the study in the departments of the Clinical Center of Sechenov University.

2. Conducting instrumental examinations (analysis of exhaled air (time-of-flight mass spectrometer with proton transfer ionization and glow discharge emission spectrometry), sphygmometry, single-channel ECG recording, bicycle ergometry, CT of coronary arteries with contrast).

3. Preparation of the obtained material for subsequent statistical processing. Statistical analysis of the obtained data.

4. Writing publications

8. Methods of the planned study (method of statistical processing of results).

The study plans to use statistical methods, including descriptive statistics, student test, chi-square test, ANOVA test and Pearson correlation test. Statistical processing of the obtained data materials will be carried out using the Statistica 12 program (StatSoft, Inc. (2014). STATISTICA (data analysis software system), version 12. www.statsoft.com).

9. Expected research result.

To create an optimal multifactorial model that determines the optimal examination of ischemic heart disease patients at rest and at peak physical exertion test. Additionally, to improve the diagnostic accuracy of the standard stress ECG test in detecting coronary insufficiency.

10. Calendar deadlines for completing the work. The work is supposed to be completed in accordance with the individual plan that was approved and agreed upon.

1. October 2023 – June 2024 (Patient recruitment)
2. June 2024 – September 2024 (Statistical analysis of results)
3. September 2024 – June 2025 (Interpretation of statistical results, writing publications)
4. June 2025 – September 2025 (Dissertation writing)

11. References

2. Russian Society of Cardiology (RSC) . 2020 Clinical practice guidelines for Stable coronary artery disease. *Russ J Cardiol*. 2020;25(11):4076. doi:10.15829/29/1560-4071-2020-4076
3. Cardiovascular diseases (CVDs). Accessed January 8, 2025. <https://www.who.int/news-room/fact-sheets/detail/cardiovascular-diseases-cvds>

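### Post-exercise breath and single-lead ECG are taken when the test stops, at a load that may differ between groups, and the readable plan does not account for load, so exertion may be read as ischaemia.

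*Protocol*

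**What the plan says.** Protocol section 4 (Research design), examination 2, states that "patients undergo a bicycle ergometry study, according to the Bruce protocol or the modified Bruce protocol". It gives no rule for who follows which protocol. The first post-exercise breath sample is timed from the end of the test: "immediately after stopping the load test, patients undergo a repeated study of exhaled air". For the second, "after 3 minutes a repeated analysis of exhaled air is carried out, also for 1 minute". Neither sample is tied to a workload, duration or heart rate. Examination 4 in the same section times the single-lead ECG and pulse wave in the same way, before the test and as soon as it ends.

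The exclusion criteria in section 5 remove patients for "Failure to complete the stress test due to reasons unrelated to cardiac conditions". What counts as completing the test is not defined.

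Section 6 lists the breath comparison among the primary endpoints. Item 2 is to take compounds from patients with a perfusion defect and "compare them with individuals without stress-induced myocardial perfusion defect after a physical stress test, and compare them with rest results as independent variables". Item 3 does the same for single-lead ECG parameters. Both add machine-learning models of diagnostic accuracy.

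The SAP's methods paragraph names Welch t or Mann-Whitney tests for two groups, ANOVA or MANOVA, multinomial logistic regression, Lasso and machine learning. It names no covariate and does not mention workload, exercise duration, heart rate or exercise protocol.

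**The concern.** Groups are defined by a pharmacological CT perfusion test, but the stimulus for the breath sample is exercise. If the amount of exercise differs by group, a compound that responds only to exertion will also differ by group.

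The plan leaves room for this in three ways: sampling follows the end of the test and not a set load; two exercise protocols are allowed; and the exclusion rule keeps early stops for cardiac reasons while removing other early stops. Early cardiac stops could plausibly be more common in the defect group.

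Subtracting the resting sample removes stable differences between people but not a difference in exercise dose. Adjusting for age or pre-test probability would not remove it either, because the difference arises during the test.

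At stake is the goal in section 3, to make the exercise test more accurate by adding breath and single-lead ECG. If a post-exercise marker mostly repeats the load reached, it adds less to the exercise test than its own AUC suggests. The analysis as described cannot show whether that is so.

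**Working it through.** **The plan's own figure.** The plan gives no power, effect size or SD for this comparison. The only figure to reproduce is the total, 31 + 49 = 80, which agrees with section 5.

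**Inputs from the documents.** Group sizes are 31 (perfusion defect) and 49 (no defect), from Protocol section 4. The significance level is 0.05, from the SAP; sidedness is not stated, and two-sided is assumed here. The two-group test has no covariates (SAP).

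**Assumed inputs.** The documents give neither of these, so a range is shown.
- d: how much lower the mean load is in the defect group, in SD.
- r: the within-group correlation between load and the compound.

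The compound is assumed to have no link to ischaemia other than through load.

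**Formulas.**
1. Standard error of the group difference, in SD units: sqrt(1/31 + 1/49) = 0.229.
2. Spurious shift = r × d.
3. Chance of p<0.05 = Φ(shift/SE − 1.96) + Φ(−shift/SE − 1.96).
4. Apparent AUC produced by load alone = Φ(r × d / √2).

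**Worked case, d = 0.5, r = 0.5.** The shift is 0.25 and 0.25/0.229 = 1.09. The chance of p<0.05 is Φ(−0.87) + Φ(−3.05) = 0.192 + 0.001 = 19.3%. The AUC is Φ(0.25/1.414) = 0.57.

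**Range: chance of p<0.05 for one compound (apparent AUC).**

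| d | r = 0.3 | r = 0.5 | r = 0.7 |
|---|---|---|---|
| 0.3 | 6.8% (0.53) | 10.0% (0.54) | 15.0% (0.56) |
| 0.5 | 10.0% (0.54) | 19.3% (0.57) | 33.2% (0.60) |
| 0.8 | 18.2% (0.57) | 41.4% (0.61) | 68.4% (0.65) |
| 1.0 | 25.8% (0.58) | 58.7% (0.64) | 86.2% (0.69) |

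At d = 0 the rate is the nominal 5%.

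**Check by simulation.** With 20,000 simulated trials per cell, the Welch t-test rates agree with the table to within about 1.5 percentage points. With load as a covariate, the rate is 4.5% to 5.2% in every cell. That recovery is built into the simulation, where load is the only driver of the compound and is measured without error. Real adjustment would be less complete.

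**Scale.** The difference detectable with 80% power at these group sizes is (1.96 + 0.84) × 0.229 = 0.64 SD. The spurious shift is 0.09 SD at the mild end of the table (0.3 × 0.3), 0.25 SD in the worked case and 0.56 SD at d = 0.8, r = 0.7.

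No separate calculation was made for single-lead ECG. The timing argument is the same, but the size is not estimated.

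**The case against.** The strongest reply is that no imbalance has been shown. A reader might infer from the exclusion rule that patients with a defect are in fact sampled at lower load. The documents do not support that: they give no workload, heart rate or stopping data by group. Exclusion 2 refers to cardiac conditions in general, so early cardiac stops may also occur without a perfusion defect. The cohort has a pre-test probability of 1% to 33%, with prior infarction, diabetes, respiratory disease and musculoskeletal limits to exercise kept out, so early stops may be few. Nothing ties the choice of exercise protocol to the CT result. All of this stands, and it limits the point to a possible bias.

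The second reply is that load is partly a consequence of ischaemia. A marker that works through reduced exercise capacity can still classify patients, and the endpoints concern diagnostic accuracy. A reader might infer that such a marker could not serve the study's goal, or that no ischaemia signal should be claimed unless it survives adjustment. Neither follows. Adjustment can remove real signal, and for single-lead ECG, adjusting for peak heart rate may remove part of what the device measures. What remains is that added value over the exercise test has to be measured against what that test already gives.

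Third, resting breath and resting single-lead ECG are already recorded, and item 2 already includes "compare them with rest results as independent variables". The resting samples are indeed unaffected by load. A change from rest is not.

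Finally, part of the SAP was not available to read, so an adjustment stated there cannot be ruled out. The available paragraph does allow multivariable methods where appropriate, but names no load variable.

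**Conclusion.** The point holds as a possible bias that the readable plan does not address. Post-exercise breath and single-lead ECG follow the end of the test, load may differ between groups, and no described analysis relates the results to load. A post-exercise group difference could therefore partly reflect exertion.

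Its size depends on two quantities that the documents do not give. For one compound without an ischaemia effect, the chance of p<0.05 is about 7% (d = 0.3, r = 0.3), 10% (d = 0.3, r = 0.5), 19% (d = 0.5, r = 0.5), 41% (d = 0.8, r = 0.5) and 68% (d = 0.8, r = 0.7). At the mild end the effect is minor. These figures assume a two-sided 0.05 test and a compound driven by load but not otherwise by ischaemia.

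The remedy is specific and directly tests the stated goal, so it is worth making even though the imbalance is unproven.

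**What to change.** In the SAP:

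- Confirm that the exercise protocol used, peak workload or exercise duration, and peak heart rate were captured from the ergometry, and report them by group.
- For endpoint 2, keep the unadjusted comparison and add a sensitivity analysis adjusted for exercise load and exercise protocol.
- For the machine-learning results, including those using post-exercise single-lead ECG, report a benchmark model with the ergometry variables alone and the gain in AUC from adding breath or single-lead ECG to it.
- Show the resting-sample comparison separately, as the load-free result.
- State in advance that a post-exercise signal that disappears on adjustment will be interpreted with caution, and not as automatically non-ischaemic.

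No change to the exercise test or its conduct is proposed.

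The cost is a little more analysis and an adjusted estimate that is conservative. A reader might infer that this is a matter of wording only, but no readable text says that the ergometry variables were recorded. The recruitment window in section 4 ended on 10.06.2024, a week before the document date of 17.06.2024. If the variables were not captured, the adjusted analysis and the benchmark are not available, and the report should say so as a limitation.

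### Participants are excluded after enrolment when a test under study fails, so accuracy describes only those in whom the test worked, and valid data for other endpoints may be lost

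*Protocol*

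**What the plan says.** Protocol section 5 has two lists. The non-inclusion list (17 items) governs entry. The separate Exclusion Criteria list has four items, of which the first two are "Poor recording quality of single-channel electrocardiogram (ECG) and/or plethysmography data" and "Failure to complete the stress test due to reasons unrelated to cardiac conditions". The other two are withdrawal of consent and conditions that arise or are found after enrolment.

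Both tests named in items 1 and 2 are themselves under evaluation. Section 6 gives as primary endpoint 1 "Assessing the diagnostic accuracy of the stress electrocardiography in the diagnosis of ischemic heart disease", and under endpoint 3 it states "Machine learning model will be used to assess the diagnostic accuracy of the single-lead ECG with pulse wave function".

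Section 4 fixes the order of procedures:

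- **Blood:** "On the morning of study enrollment, a single 10 mL venous blood sample will be collected via peripheral venipuncture", from all participants.
- **Breath:** sampled at rest first ("After the procedure of exhaled air analysis in PTR TOF-1000, patients undergo a bicycle ergometry study"), then again after exercise ("immediately after stopping the load test, patients undergo a repeated study of exhaled air").
- **Single-lead ECG:** "Before and immediately after the exercise test, all patients are scheduled to have a single-channel ECG and pulse wave recorded".
- **CTP, the reference standard:** planned for everyone.

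The protocol's statistical section and the available SAP text contain no rule for non-evaluable tests and no endpoint-specific analysis sets. Part of the SAP was not available for this review, so that silence is confirmed only for the text supplied.

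**The concern.** A diagnostic accuracy estimate should describe the people in whom the test is attempted. If those with unusable recordings or unfinished exercise tests are removed and not counted, a reader cannot tell how far the reported sensitivity and specificity carry over to practice, where such failures occur. The estimates may overstate accuracy, but this cannot be established without the failure rate in each CTP group.

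There is a second cost. The criteria are worded for the participant, not for one endpoint. On the natural reading, a noisy single-lead trace also removes that person's lipids, ApoB, lipoprotein(a), CRP, IL-6, breath data and 12-lead stress ECG, none of which depend on the quality of that trace.

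**Working it through.** **1. When the items act.** The single-lead recordings and the stress test are study procedures, so items 1 and 2 can be known only after enrolment. People already known to be unable to exercise for musculoskeletal reasons are covered by non-inclusion item 14. Item 2 covers non-cardiac reasons only; tests stopped for cardiac reasons are not excluded by it.

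**2. Which data remain valid in an excluded person.**

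| | Item 1 (poor single-lead recording) | Item 2 (exercise not completed) |
|---|---|---|
| Blood, endpoints 4-7 | valid | valid |
| Resting breath | valid | valid |
| Post-exercise breath | valid | not claimed as valid: incomplete exercise changes it |
| 12-lead stress ECG | valid | failed test |
| Resting single-lead ECG | failed test if this is the poor recording | valid |
| Post-exercise single-lead ECG | failed test if this is the poor recording | not claimed as valid, same reason |

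**3. The plan's own figure.** The planned groups are 31 with and 49 without a perfusion defect, and 31 + 49 = 80 agrees with section 5. The available text gives no power, precision target, failure rate or expected accuracy, so nothing further can be reproduced.

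**4. Accuracy under assumed failure rates.** Let q1 and q0 be the non-evaluable shares in the CTP-positive and CTP-negative groups. Assume Se = Sp = 0.80 among evaluable people (Youden 0.80 + 0.80 - 1 = 0.60).

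- All failures counted negative: Se = 0.80(1 - q1); Sp = 0.80(1 - q0) + q0.
- All failures counted positive: Se = 0.80(1 - q1) + q1; Sp = 0.80(1 - q0).

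For example, at q1 = q0 = 0.10, all-negative gives Se = 0.80 × 0.90 = 0.72 and Sp = 0.72 + 0.10 = 0.82.

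| q1 / q0 | All negative, Se/Sp | All positive, Se/Sp | Youden (negative; positive) |
|---|---|---|---|
| 5% / 5% | 0.76/0.81 | 0.81/0.76 | 0.57; 0.57 |
| 10% / 10% | 0.72/0.82 | 0.82/0.72 | 0.54; 0.54 |
| 20% / 20% | 0.64/0.84 | 0.84/0.64 | 0.48; 0.48 |
| 5% / 15% | 0.76/0.83 | 0.81/0.68 | 0.59; 0.49 |
| 15% / 5% | 0.68/0.81 | 0.83/0.76 | 0.49; 0.59 |

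With equal rates the Youden index is 0.60(1 - q) under either rule. If the failed tests would have been as accurate as the others, Se and Sp stay at 0.80. Outer bounds at 10%, which no single rule can produce: all failures incorrect gives 0.72/0.72, and all correct gives 0.72 + 0.10 = 0.82 for both.

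**5. Loss for the blood endpoints.** For a two-sample t-test (two-sided alpha 0.05, 80% power, noncentral t), the detectable standardised difference is d = 0.651 with 31 v 49. With an assumed 10% lost (31 × 0.90 = 27.9, 49 × 0.90 = 44.1, so 28 v 44) it is d = 0.687. This applies only if 80 is the number enrolled; if 80 is the number analysed, there is no such loss.

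**The case against.** The protocol's single goal is to improve the 12-lead stress test by adding breath and single-lead ECG data. It expects one multifactorial model, and the SAP lists the McNemar test, which is paired. Such analyses need complete data in the same people, so a common complete-data cohort is defensible. This stands for combined and paired analyses, and the fix keeps such a set for them. It does not justify dropping blood results from single-endpoint comparisons or leaving failures uncounted.

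The protocol does not expressly say that an excluded person's blood or breath data are discarded, and the unavailable part of the SAP might contain a rule. Both points stand as limits: the data loss is the natural reading, not a stated fact. The restriction on endpoints 1 and 3 does not depend on it.

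The accuracy figures rest on assumed rates, and the fall in Youden index follows mechanically from giving every failed test the same result. That is correct. They show what uncounted failures could mean and are not evidence of bias in this study.

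The exact group sizes of 31 and 49, given although group membership is known only after CTP, suggest that 80 may be the analysed number. If so, the power loss disappears. Even otherwise it is small.

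**Conclusion.** The concern holds. Items 1 and 2 are written as participant-level exclusions triggered by failure of a test whose accuracy is a primary endpoint, and nothing in the available text repairs this. The main consequence is about whom the accuracy describes: only people in whom the test worked, with no requirement to say how many others there were.

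Its size cannot be known from the documents. Under the assumed 0.80 accuracy and equal failure rates of 5% to 20%, sensitivity falls to between 0.76 and 0.64 when failures count as negative, and specificity falls by the same amount when they count as positive. It is no change at all if failed tests would have been equally accurate. The possible cost to the blood endpoints is minor (d from 0.65 to 0.69 at an assumed 10% loss) and conditional on 80 meaning enrolled. The change should be made, with medium confidence, because part of the SAP could not be seen.

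**What to change.** Replace items 1 and 2 with endpoint-specific analysis rules:

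- Keep every consenting participant who has a CTP result, and analyse each endpoint in all who have usable data for it.
- After an incomplete stress test, allow post-exercise breath and post-exercise single-lead ECG to be left out of their own endpoints. Keep the pre-exercise recordings for rest analyses.
- Use a common complete-data set, named as such, for any combined model and for paired comparisons between tests.
- Report the number of non-evaluable single-lead ECGs, and of stress tests not completed for non-cardiac reasons, by CTP group.
- Keep evaluable-only accuracy as the main estimate. Add sensitivity analyses counting all non-evaluable tests as negative and then all as positive, with all-incorrect and all-correct labelled as bounds only.

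For the counts to be reproducible, it would also help to define poor recording quality, have it judged blind to CTP, and say whether one poor recording of the two makes the test non-evaluable. State whether 80 is counted before or after exclusions.

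The cost is protocol and SAP wording and a little more analysis, with no extra procedure. Sensitivity or specificity will look less favourable in the added analyses. Denominators will differ across endpoints, so separate accuracy figures are directly comparable only in the common set. Planned recruitment ended on 10.06.2024, before the document date of 17.06.2024; for anyone already excluded without CTP, only counts and reasons can be reported.
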